# 6. Study Intervention Administered

# 6.1. Preparation/Handling/Storage/Accountability

The study intervention will be manufactured at collaborative blood bank units according to specified procedures. Briefly, potential donors of convalescent plasma will be evaluated at the blood-bank according to local SOP for plasma donors, regulated by "Blodforskriften". Male donors with previous transfusion history and all female donors will be screened for HLA I and HLA II antibodies. As a rule, plasma will be collected by apheresis in volumes of 600-850ml

dependent on body weight, and later split into therapeutic units of 200-350 ml before freezing according to local SOP. Plasma derived from a full-blood donation may also be used.

At the coordinating institution

- 1. The investigator or designee must confirm that appropriate temperature conditions have been maintained during transit for all study intervention received and any discrepancies are reported and resolved before use of the study intervention.
- 2. All study intervention must be stored in a secure, environmentally controlled, and monitored (manual or automated) area in accordance with the labeled storage conditions with access limited to the ambulatory team.
- 3. Only participants enrolled in the study may receive study intervention and only authorized site staff may supply or administer study intervention. Administration will follow SOP for transfusion. Blood pressure, pulse, respiratory frequency and temperature will be taken at pre-specified time-points (before transfusion, at the end of transfusion, 15 minutes after transfusion and 1 hour after transfusion.
- 4. Authorized site staff must monitor participants closely for 1 hour after study intervention for signs of adverse events. SAEs (Section 8.3) and other serious events (Section 8.3.5) will be reported immediately to the Medical Monitor, and an adverse events form will be recorded at the end of the study participation.
- 5. The coordinating investigator is responsible for study intervention accountability, reconciliation, and record maintenance (i.e., receipt, reconciliation, and final disposition records).

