## 2.3. Benefit/Risk Assessment

Convalescent plasma has not yet been shown to be safe and effective as a treatment for COVID-19. A pre-publication study on safety in 5000 patients indicates that convalescent plasma treatment is safe, even to critically ill COVID-19 patients (Joyner et al 2020).

Potential Risk of Clinical	Summary of Data/Rationale	Mitigation Strategy
Significance	for Risk	Preparation of plasma
Risks commonly associated with transfusion	Low frequency, but higher risk for transfusion associated complications among elderly	according to EU guidelines for COVID- 19

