## 5.3. Study Intervention and Concomitant Therapy

Convalescent plasma will be collected from volunteer non-paid donors who recovered from a CoV-2 infection. Collection volume will be split to therapeutic units of 200-300 ml. Previous medical therapy will be continued with no interruption.

	Т		
ARM Name	COVID-19 convalescent plasma		
Intervention	ISBT E9735 CONVALESCENT PLASMA CPD/XX/<=-18C COVID-19		
Name	ISBT E9736 Apheresis CONVALESCENT PLASMA CPD/XX/<=-18C COVID-19		
	ISBT E9754 Apheresis CONVALESCENT PLASMA ACD-A/XX/<=-18C 1st container COVID-19		
	ISBT E9755 Apheresis CONVALESCENT PLASMA ACD-A/XX/<=-18C 2nd container COVID-19		
	ISBT E9756 Apheresis CONVALESCENT PLASMA ACD-A/XX/<=-18C 3rd container COVID-19		
	ISBT E9757 Apheresis CONVALESCENT PLASMA ACD-A/XX/<=-18C 4th container COVID-19		
Туре	Biologic		
Dose Formulation	200-300 ml		
Unit Dose Strength(s)	High titer, defined as virus neutralization assay titer >1:160 or equivalent in accordance with EBA (to be confirmed)		
Dosage Level(s)	1 dose at inclusion		
Route of Administration	I.V. transfusion		
Use	Clinical indication		
IMP and NIMP	Investigational Medicinal product (IMP)		
Sourcing	COVID-19 convalescent plasma from voluntary non-paid donors at the following Norwegian blood banks: Oslo University Hospital, Haukeland University Hospital, St. Olav's Hospital		
Packaging and Labeling	Following local SOP for plasma-labeling, using the correct ISBT code		

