# 6.6. Concomitant Therapy

Any medication or vaccine that the participant is receiving at the time of enrollment or receives during the study must be recorded along with:

- Reason for use
- Dates of administration including start and end dates
- Dosage information including dose and frequency

The Medical Monitor should be contacted if there are any questions regarding concomitant or prior therapy.

No medication is contraindicated.

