## Hypotensive transfusion reaction

This reaction is characterized by hypotension defined as a drop in systolic blood pressure of  $\geq$ h30 mm Hg occurring during or within one hour of completing transfusion **and** a systolic blood pressure  $\leq$  80 mm Hg. Most reactions do occur very rapidly after the start of the transfusion (within minutes). This reaction responds rapidly to cessation of transfusion and supportive treatment. This type of reaction appears to occur more frequently in patients on ACE inhibitors. Hypotension is usually the sole manifestation but facial flushing and gastrointestinal symptoms may occur.

All other categories of adverse reactions presenting with hypotension, especially allergic reactions, must be excluded. The underlying condition of the patient must also be evaluated as a possible explanation for the hypotension.

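### The Section 6.1 vital-sign schedule has no blood pressure reading during the infusion, when Appendix 4 says most hypotensive reactions occur

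*Protocol*

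**What the plan says.** Section 6.1, item 3, refers to an SOP for transfusion and then gives the times for blood pressure, pulse, respiratory frequency and temperature. They are taken "at pre-specified time-points (before transfusion, at the end of transfusion, 15 minutes after transfusion and 1 hour after transfusion". Item 4 requires close monitoring, and sets it for the hour after the intervention.

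Appendix 4 defines the hypotensive transfusion reaction by a fall in systolic pressure together with a low absolute value, during the transfusion or within an hour of completing it. On timing: "Most reactions do occur very rapidly after the start of the transfusion (within minutes"). On presentation: "Hypotension is usually the sole manifestation but facial flushing and gastrointestinal symptoms may occur". On management: "This reaction responds rapidly to cessation of transfusion and supportive treatment". On risk: "This type of reaction appears to occur more frequently in patients on ACE inhibitors".

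Four other places bear on the point:

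- Section 6.4 has the transfusion terminated if an adverse event occurs.
- Section 8.2 provides for standard clinical observation both during and after the transfusion, without naming a blood pressure reading.
- Section 8.3.6 makes the Appendix 4 transfusion reactions adverse events of special interest.
- The schedule of activities (Section 1.2) lists the transfusion on day 0 and gives no vital-sign times around it.

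**The concern.** A reaction that usually shows itself only as low blood pressure is found by measuring blood pressure. The protocol says most such reactions begin within minutes of the start, yet after the pre-transfusion reading the next listed one is at the end.

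The stopping rule in Section 6.4 helps only if the event is found while plasma is still running. If a drop is first seen at the end of the infusion, the whole unit has been given and stopping is no longer an option. A drop that came and went before then might never be recorded, although these reactions are adverse events of special interest and, under Section 10.1.4, among the events reviewed for pausing or stopping the study.

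The population makes this more relevant. The risk table in Section 2.3 describes the general transfusion risks as "Low frequency, but higher risk for transfusion associated complications among elderly". ACE inhibitors, named in Appendix 4 as a likely risk factor, are not held back: Section 5.3 states "Previous medical therapy will be continued with no interruption" and Section 6.6 states "No medication is contraindicated". Section 5 notes a high proportion of dementia among care-home residents, while Sections 8.3 and 8.3.2 rely largely on reports and verbal questioning to detect adverse events. Some participants may not be able to say that they feel unwell.

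**Working it through.** The protocol states no figure here that needs reproducing. The check sets the reading times beside the described course of the reaction and then counts readings.

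**Times compared**

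| Period | Readings listed in Section 6.1 | What Appendix 4 says of the hypotensive reaction |
|---|---|---|
| Before the infusion | 1 | Not applicable |
| From the start until just before the end | 0 | Within the definition; most reactions begin here, within minutes of the start |
| End of infusion to 1 hour after | 3 (end, 15 minutes, 1 hour) | Within the definition |

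The definition covers the infusion and the following hour. Three of the four readings cover the second part. None covers the first, where most reactions are said to begin.

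**Search for a reading elsewhere.** Sections 6.3, 6.4, 8.2 and 8.3, the schedule of activities and Appendices 3 and 4 contain no blood pressure reading between the start and the end of the infusion.

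**Could the 15-minute reading be meant from the start?** Possibly, but the text does not say so. It stands between the end-of-transfusion and 1-hour-after readings and is worded as following the transfusion. If the start was meant, the wording needs correcting.

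**Size of the change**

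- Planned total: 506 participants (Section 9.2), randomized 1:1, so the plasma arm is 506 / 2 = 253.
- Listed readings per transfused participant: 1 + 0 + 3 = 4, in total 253 × 4 = 1,012.
- With one reading added: 5 per participant, in total 253 × 5 = 1,265.
- Difference: 1,265 − 1,012 = 253 readings.

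**What cannot be computed.** The number of reactions that would be found late equals the number transfused, times the reaction rate, times the share that begin early and without other signs. The protocol gives neither a rate nor that share as a number. It also gives no infusion duration, so the delay until the end-of-transfusion reading cannot be stated.

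**The case against.** The strongest objection is that Section 6.1 hands the conduct of the infusion to an SOP, and that monitoring during a transfusion is ordinary SOP content. That the reading is absent from the list is established; that patients go unmeasured is not. This stands, and it is why the conclusion is conditional. It does not remove the point: Section 6.1 sets out the vital-sign times itself, and staff could reasonably take that list as complete.

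Second, Section 8.2 commits to observation during the transfusion, and under Section 6.3 a second staff member confirms dose and identity at dosing, so people are at the bedside around the start. Observation would catch visible reactions and may prompt a measurement. It does not reliably catch a drop with no other sign, which Appendix 4 calls the usual presentation.

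Third, Appendix 4 gives case definitions, not a monitoring schedule, so nothing in Section 6.1 breaks a stated requirement. That is correct. This is a weak design choice judged by the protocol's own description of the reaction, not a contradiction.

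Fourth, a drop that persists to the end would still be found, recorded and given supportive treatment. That is also correct. What is lost is the chance to stop the infusion and the record of any drop that resolved before the end. The definition is also narrow (a fall of 30 mm Hg or more and a systolic pressure of 80 mm Hg or less), and the risk table describes transfusion risks as infrequent. Few participants may be affected.

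**Conclusion.** The point holds. Of the four listed readings, none falls during the infusion, and the protocol itself places most hypotensive reactions in its first minutes. Unless the SOP requires a reading or bedside observation prompts one, a drop without other signs would probably be found only at the end.

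The effect is confined to patient safety in the plasma arm and to the recording of one type of adverse event of special interest. The analysis of mortality is unaffected. The number of patients concerned is unknown. Confidence is medium because the SOP has not been seen. The change is worth making because the patients are frail and it costs very little.

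**What to change.** Add to the list in Section 6.1 one blood pressure and pulse reading shortly after the start of the infusion, for example at about 15 minutes; the exact time is for the sponsor to set. If the transfusion SOP already requires such a reading, state it in Section 6.1. If the existing 15-minute reading was meant to count from the start, reword it so that this is clear.

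The cost is one added time-point in the text and one reading per transfused participant, about 253 in all. Under Section 6.3 the ambulatory team gives the plasma itself, so no further visit or staff is needed.

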# 1.2. Schedule of Activities (SoA)

[figure not shown]
Procedure	Screening (up to intervention	Inter vention (day 0)		0	bserva	tion Peri	od (day	1-60)	
	day)	0	1	3	7	14	21	28	60
Informed consent	Х								
Inclusion and exclusion criteria	Х								
Randomization	Х								
Demography	Х								
Height and weight	Х								
Medical status and co- morbidities	Х								
Current medication	Х								
Blood samples*		X	Х	Х	Х	Х			
Oropharynx samples**		X	Х	Х	Х	Х	Х	Х	
Clinical assessment***		X	Х	Х	Х	Х	Х	Х	
Mortality registration								X	Х
Study intervention (plasma transfusion)		X							
AE and SAE review									Х

Activities are scheduled as presented in table and flow-chart below.

\* Blood: Hemoglobin, thrombocytes, leukocytes with differential count, CRP, anti-Spike IgG.

\*\*Oropharynx: RTPCR SARS-CoV-2.

\*\*\* Registration of oxygen therapy at all care homes, NEWS score where implemented in the care home routines.

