## 4. Study Design

## 4.1. Overall design

The *Norwegian convalescent plasma in COVID-19 study* is an unblinded randomized controlled trial investigating the effects of convalescent plasma on the clinical course of disease in patients with active COVID-19.

Patients referred to or staying at nursing homes with newly diagnosed symptomatic COVID-19 infection and a positive SARS-CoV-2 PCR in a respiratory tract sample will be randomized 1:1 to be given:

-Local standard supportive treatment alone

OR

-Local standard supportive treatment AND a single dose of COVID-19 convalescent plasma transfusion

Participants will be followed up on-site for up to 28 days by clinical assessments, respiratory tract sampling for SARS-CoV-2 PCR and biochemical testing at a pre-specified schedule. Participants will be followed up remotely for up to 60 days after intervention to assess mortality.

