## 8.3.1. Frequency for Collecting AE and SAE Information

All SAEs will be collected from the start of intervention until the end of the study period (day 60). Medical occurrences that begin before the start of study intervention but after obtaining informed consent will be recorded as Medical History/Current Medical Conditions, not as AEs.

All SAEs will be recorded and reported to the medical monitor immediately and under no circumstance should this exceed 24 hours. The investigator will submit any updated SAE data to the sponsor within 24 hours of it being available.

Investigators are not obligated to actively seek information on AEs or SAEs after conclusion of the study participation. However, if the investigator learns of any SAE, including a death, at any time after a participant has been discharged from the study, and he/she considers the event to be reasonably related to the study intervention or study participation, the investigator must promptly notify the sponsor.

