## 10.1.4. Committees Structure

## **Data Monitoring Committee**

- Participant safety will be continuously monitored by the Sponsors designated Data Monitoring Committee (DMC).
- In addition, an early aggregated safety data review will be performed, the goal of which is to allow for a cautious, stepwise approach to [intervention] administration. An initial safety review for this study is planned for the first 50 participants/ 20 % of participants who are dosed and have provided safety data for 14 days after administration of convalescent plasma.
- All safety data collected will be summarized and reviewed by the DMC for agreement of next steps.
- In particular, data will be reviewed by the Sponsor for identification of the following events that would potentially contribute to a requirement to stop or pause the study.
  - Any deaths, regardless of causality
  - Any SAE
  - Any AESI (see table in Appendix 4)

- If a pausing rule is met, a decision will be made, based on the review, as to whether enrollment in the study will be allowed to resume.
- Safety data will also be included in the Norwegian Health Directorate's system for Hemovigilance monitoring (https://www.helsedirektoratet.no/rapporter/overvaking-av-blod-i-norge)

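### Non-serious adverse events have no scheduled collection before day 60, although on-site visits end at day 28 and the Data Monitoring Committee is to review adverse events much earlier

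*Protocol*

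**What the plan says.** Two places in the protocol give a time for AE recording, and both put it at the end.

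- Section 6.1, item 4: "an adverse events form will be recorded at the end of the study participation".
- Section 1.2, schedule of activities: the row "AE and SAE review" carries one mark, in the day-60 column as extracted. Days 0, 1, 3, 7, 14, 21 and 28 have none in that row, although clinical assessment is marked on all of them.

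On contact with participants, section 4.1 says "Participants will be followed up on-site for up to 28 days by clinical assessments", and then "Participants will be followed up remotely for up to 60 days after intervention to assess mortality".

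Serious events are handled separately. Item 4 of section 6.1 also says "SAEs (Section 8.3) and other serious events (Section 8.3.5) will be reported immediately to the Medical Monitor". Section 8.3.1 collects serious adverse events (SAEs) from the intervention to day 60, with a 24-hour reporting limit.

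The safety reviews come earlier than day 60. Section 9.4 has the DMC look at the whole of the safety data, AEs among them, at 20%, 50% and 70% inclusion. Section 10.1.4 adds an initial review of the first 50 (or 20%) participants who are dosed and "have provided safety data for 14 days after administration of convalescent plasma".

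AE incidence is the only safety endpoint in section 3, listed as exploratory.

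**The concern.** A non-serious AE in the first weeks is most reliably recorded when staff see the participant. The protocol has seven such occasions up to day 28 and attaches AE review to none of them. The review is placed at a time when contact is remote and described as being for mortality. Section 8.3.2 prefers open questioning of the participant, while section 5 describes a population with much dementia. Recall after up to two months is a weak source here.

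Two things are at stake. The DMC is asked to judge AE data that no scheduled step supplies by the time it meets. And the AE incidence reported at the end may be incomplete, possibly to a different degree in the two arms. The one prescribed close watch, "Authorized site staff must monitor participants closely for 1 hour after study intervention for signs of adverse events", follows the transfusion and so covers the plasma arm only. Controls in this open-label trial have no matching check.

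**Working it through.** **1. Do other sections set an earlier time for non-serious AEs?**

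| Section | What it provides | Time set for non-serious AEs? |
|---|---|---|
| 8.2 | Events, including delayed ones, go on the AE form | No |
| 8.3 | Investigator and nursing-home staff detect and record; caregivers may report | No |
| 8.3.1 | Collection window and 24-hour limit | No, SAEs only |
| 8.3.3 | Active follow-up at later visits | Only after a first report exists |
| 8.3.6 | Transfusion reactions go to national hemovigilance | No time for the trial form |

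The only time attached to the AE form is the one in section 6.1.

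**2. Lag against the 14-day review.** A form recorded at day 60 comes 60 − 14 = 46 days after the participant reaches the 14-day mark.

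**3. Forms on hand at the DMC reviews (illustration).** The protocol gives no accrual curve. Assume uniform accrual and that the planned 365 days (1 July 2020 to 30 June 2021) include the last participant's 60 days, so accrual takes 365 − 60 = 305 days. At inclusion fraction f, the share of included participants who have passed day 60 is 1 − 60/(305f):

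- f = 0.20: 1 − 60/61 = 2%
- f = 0.50: 1 − 60/152.5 = 61%
- f = 0.70: 1 − 60/213.5 = 72%

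If the first fifth took twice as long to recruit (122 days), the first figure would be 1 − 60/122 = 51%. Forms closed early by death or withdrawal would add to these shares.

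**4. Deaths before a day-60 review.** First the plan's own design figures (section 9.2: 30% against 18% mortality, hazard ratio 0.60, 80% power, two-sided 5%, 1:1):

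- Events (Schoenfeld): (1.960 + 0.842)² / (0.25 × (ln 0.60)²) = 120.3, rounded up to 121.
- N: 120.3 / 0.24 = 501.3, rounded up to 502, where 0.24 = (0.30 + 0.18)/2.
- With inflation: 502 × 1.008 = 506, or 253 per arm.

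The stated figures reproduce. Taking the mortality assumption to refer to the 28-day primary endpoint:

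- Control: 253 × 0.30 = 75.9 deaths
- Plasma: 253 × 0.18 = 45.5 deaths
- Total: 121.4 of 506, or 24%

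Section 2.2 gives care-home case fatality of 15% to 50%. Using that range for controls with the same 40% relative reduction, the share dead by day 28 is (0.15 + 0.09)/2 = 12% to (0.50 + 0.30)/2 = 40%.

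**5. Who could be questioned.** Under the design alternative, 70% of controls and 82% of plasma participants are alive at day 28, a gap of 12 points. If mortality is equal, the gap is zero.

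**The case against.** A reader might infer that all adverse events wait until day 60. The protocol does not support that. SAEs and other serious events are reported immediately or within 24 hours, staff watch each transfused participant for an hour, and sections 8.2 and 8.3 oblige staff to detect and register events. Section 6.1 times the form; it does not say that detection or source notes wait for it.

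A reader might also infer that the 14-day review would have no data. Section 10.1.4 names deaths, SAEs and adverse events of special interest as the events that could pause or stop the study. Deaths are SAEs, and Appendix 4 heads the special-interest events as serious, so these mostly have prompt routes. What is not assured is the non-serious part.

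Nor is the 12-point gap a loss of AEs. It is the assumed mortality difference, showing who could be asked in person. Caregivers and staff can report, and for someone who dies the end of participation can be read as the date of death, so the form could be completed then from records.

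Finally, the schedule is an extracted table, and a mark spanning several columns could have been lost. That is a fair caution for section 1.2 alone, but section 6.1 says the same in running text.

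These points confine the finding to non-serious AEs. They do not supply an earlier scheduled collection for those events, and they leave the conflict with section 9.4 in place.

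**Conclusion.** The point holds for non-serious AEs. The protocol fixes their recording at the end of participation, after on-site follow-up has stopped and after about 24% of participants (12% to 40% over the protocol's own fatality range) are expected to have died. This conflicts with DMC reviews that include AEs at 20%, 50% and 70% inclusion and with the early review of 14-day data, which a day-60 form misses by 46 days.

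Under-recording is a plausible risk, not a demonstrated result, and no number of lost events follows from the document. The risk may differ between arms, because the one-hour watch exists in the plasma arm only and because survival differs if plasma works as assumed. The conclusion rests on section 6.1 as written, on the schedule as extracted, and on reading the 30% and 18% as 28-day mortality. Serious events and deaths are outside it.

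This should be corrected. An analysis plan cannot recover events that were never recorded.

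**What to change.** - In the schedule of activities, mark AE and SAE review at the existing on-site visits (days 0, 1, 3, 7, 14, 21 and 28) in both arms, with day 60, or death or withdrawal if earlier, as the closing review.
- Amend section 6.1 item 4 so that the AE form is opened at day 0 and updated at each of these visits. Immediate reporting of serious events stays as it is.
- Align sections 8.2 to 8.3.3 with this timing, so that the reviews in sections 9.4 and 10.1.4 draw on forms that are current when the DMC meets.
- In the same edit, reconcile section 6.1, which has the section 8.3.5 events reported immediately, with section 8.3.5, which takes them out of expedited reporting.

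Cost: revised schedule and case report form wording, and a few minutes at each existing visit. No visits are added.
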